#### **8.3.1 Disease Response Assessment**

Disease assessment will follow IWG 2006 criteria ([Section 10.6](#)) and will include CR, HI, and ORR (including CR, mCR, or any HI). Other assessments will include duration of PFS, LFS, undetectable disease assessed by MRD, DOR, and OS. Disease response assessment will be determined based on BM evaluations and a corresponding PB sample along with transfusion requirements. Bone marrow evaluations must include aspirate (when feasible), biopsy, and cytogenetics. If hematologic recovery is in progress, a repeat CBC may be done no more than 7 days after the BM evaluation for response assessment. The BM biopsy and aspirate procedure will be conducted according to local standard practice at time points shown in the SoA ([Table 1](#)).

BM and PB samples adequate for analysis must be obtained in order to confirm response. BM biopsy and aspirate and a CBC must be repeated if the BM and/or PB sample are not interpretable by the investigator. A local laboratory will be used to assess BM and PB samples. BM samples should be Wright Giemsa or May Grunwald Giemsa stained. Detailed instructions for processing BM samples will be provided in the Laboratory Manual.

BM evaluations should be performed at screening and on Day 1 of every cycle (or within a 3-day window prior to Day 1) until an mCR is achieved (BM myeloblasts  $\leq 5\%$  and decrease by  $\geq 50\%$  over pretreatment). If an mCR is achieved, without meeting CR criteria, a follow-up BM evaluation should occur on Day 1 of the next cycle (or within a 3-day window prior to Day 1) to assess or confirm the possibility of CR. Thereafter, BM evaluation may occur as clinically indicated to monitor DOR as appropriately guided by PB counts after achieving a confirmed CR

but should occur at least every 3 cycles for the first year, then as clinically indicated. Results do not have to be fully available to start study treatment for that cycle.

Response will be assessed by the investigator and derived programmatically based on the 2006 IWG criteria ([Cheson et al 2006](#)). Further details of the IWG criteria can be found in Section [10.6](#).

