## 2.0 INTRODUCTION

### 2.1 Background

Myelodysplastic syndromes (MDS) are premalignant clonal hematopoietic disorders characterized by bone marrow (BM) failure due to the production of dysfunctional, dysplastic BM cells. Primarily, these disorders affect individuals  $\geq 60$  years of age (Ma 2012). Low- and very low- risk subjects, as defined by the Revised International Prognostic Scoring System for myelodysplastic syndromes (IPSS-R; Greenberg et al 2012), are often treated with erythroid and myeloid growth factor support and carry a low risk of leukemic progression. In contrast, intermediate- to high-risk subjects with MDS have up to a 25% chance of leukemic transformation (NCCN 2022).

Intermediate- to high-risk subjects with MDS and are generally treated with hypomethylating agents (HMAs). The HMAs azacitidine (Vidaza®) and decitabine (DACOGEN®) are given as standard of care (SOC) for newly diagnosed MDS subjects with specific high-risk subtypes, and the approved schedules comprise consecutive daily dosing for 5 or 7 days in 28-day cycles. Treatment, which may continue for several months or even years, may engender significant hardship due to the 5 to 7 daily visits required each month, and the 1-hour intravenous (IV) infusion or large-volume subcutaneous injections. A possible consequence is noncompliance or premature discontinuation. In addition, the overall response rate (ORR; complete response [CR] + partial response [PR]) is approximately 16%, and overall survival (OS) is approximately 18 months (Silverman et al 2002). Thus, novel therapies that replace or augment the efficacy of HMAs or that can be formulated as a more convenient oral administration are needed to improve outcomes and extend survival for subjects with MDS.

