Results from a Phase 3, multicenter, randomized, crossover study in subjects with MDS/CMML or AML (ASTX727-02) established AUC equivalence of the FDC tablet (35 mg decitabine and 100 mg cedazuridine) with IV administered decitabine ( $20 \text{ mg/m}^2$ ). Assessment of efficacy indicated that the best response of CR was observed in 21.8% of all treated subjects and in 24.8% of subjects evaluable for response. Marrow CR was achieved in 32.3% of all treated subjects and in 36.8% of subjects evaluable for response. The ORR (CR + PR + mCR + HI) was 61.7% in all treated subjects and 70.1% in subjects evaluable for response. In addition, mCR with HI was reported in 16.5% of all treated subjects and in 18.8% of subjects evaluable for response. Sixteen subjects (12%) were not evaluable for response. With respect to the rate of subjects who were transfusion independent for  $\geq 56$ ,  $\geq 84$ , and  $\geq 112$  consecutive days at any time post-baseline for subjects who were transfusion dependent at baseline, more than half (51.9%) of the 54 subjects who were RBC transfusion dependent at baseline were RBC transfusion independent for any consecutive  $\geq 56$ -day period post-baseline. A similar overall rate of platelet TI (50%) for any consecutive  $\geq 56$ -day period post-baseline was observed for subjects with platelet transfusion dependence at baseline. Rates of RBC and platelet TI were 40.7% and 33.3%, respectively, for  $\geq 84$  consecutive days and leveled at 33.3% for  $\geq 112$  consecutive days. The overall incidence of common adverse events (AEs) of thrombocytopenia, neutropenia, anemia, and febrile neutropenia observed in Phase 2 and Phase 3 was generally similar between oral decitabine/cedazuridine and IV decitabine. Further details can be found in the oral decitabine/cedazuridine IB.

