The anti-CD47 mAb magrolimab has demonstrated encouraging data in the MDS population in combination with the HMA azacitidine (Vidaza®). Clinical studies have demonstrated that this combination has meaningful clinical activity that appears to be enhanced compared with azacitidine monotherapy in subjects with MDS. In a study investigating the clinical activity of magrolimab in combination with azacitidine in subjects with treatment-naïve intermediate- to higher-risk MDS (by IPSS-R) (Study 5F9005; [Sallman et al 2019](#)), 24 subjects were evaluable for efficacy. The ORR was 92%, with 50% achieving a CR. Complete cytogenetic response was observed in 26% of subjects who had abnormal cytogenetics at baseline. Minimal residual disease (MRD) negativity was achieved in 23% of subjects, as assessed by flow cytometry. With a median follow-up of 6.4 months, no median duration of response (DOR) had been reached, with several subjects in response over 14 months on therapy. In addition, putative CD34+CD48- leukemia stem cell progenitors were substantially reduced or eradicated by magrolimab in combination with azacitidine in responding subjects who were evaluated. Magrolimab in combination with azacitidine is currently being evaluated for survival and CR (co-primary objectives) in a large, randomized Phase 3 study (ENHANCE, NCT04313881) comparing the efficacy and safety of magrolimab plus azacitidine with that of azacitidine plus placebo (PBO) in previously untreated subjects with high-risk MDS; further details can be found in the magrolimab IB. Despite its clinical benefit, treatment with azacitidine requires chronic parenteral treatment for 5 to 7 days each month for responding subjects; this number of clinic/hospital visits is a significant burden for what is primarily an elderly population. Furthermore, an online survey that assessed treatment challenges

in subjects with MDS determined that IV/subcutaneous HMA administration resulted in pain and impacted daily activities, suggesting that an oral HMA might reduce treatment challenges for this population ([Zeidan et al 2022](#)).

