### 3.0 OBJECTIVES AND ENDPOINTS

Objectives	Endpoints
Primary	

To evaluate preliminary safety and efficacy of oral decitabine/cedazuridine in combination with magrolimab.

	

Adverse events graded according to NCI CTCAE, Version 5.0 (Section 10.5), DLTs, and CR rate.

Secondary	

To evaluate the PK profile of oral decitabine/cedazuridine and magrolimab.

	

Concentration versus time and PK parameters.

To evaluate other clinical efficacy of oral decitabine/cedazuridine and magrolimab.

	

ORR, rate of HI, duration of PFS, LFS, undetectable disease assessed by MRD, DOR, and OS.

To evaluate efficacy and safety by prespecified subgroups (eg, IPSS-M, p53 status).

	

Safety and efficacy based on molecular features (eg, IPSS-M score, p53 status).

CR=complete response; DLT=dose-limiting toxicity; DOR=duration of response; HI=hematologic improvement; IPSS-M=Molecular International Prognostic Scoring System for myelodysplastic syndromes; LFS=leukemia-free survival; MRD=minimal residual disease; NCI CTCAE=National Cancer Institute Common Terminology Criteria for Adverse Events; ORR=overall response rate; OS=overall survival; PFS=progression-free survival; PK=pharmacokinetic(s)

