#### 4.2 Scientific Rationale for Study Design

Oral decitabine/cedazuridine has been developed by Astex and is an HMA approved for use in subjects with intermediate to high-risk MDS, as well as in subjects with CMML. As discussed in Section 2.2, results from Phase 2 and 3 studies have demonstrated a positive treatment effect of oral decitabine/cedazuridine. This is a Phase 2, open-label, multicenter, non-randomized interventional study with no active comparator or control. The goal of this study is to assess the safety and efficacy of combining oral decitabine/cedazuridine with magrolimab in subjects with intermediate- to very high-risk MDS. This combination with an oral HMA may provide a safe and efficacious alternative to azacitidine in combination with magrolimab for this population while minimizing the burden of treatment for subjects and caregivers (ie, number of required clinic visits, transportation time, and complications of parenteral therapy).

Complete response was the efficacy endpoint in several Phase 1 studies with magrolimab and it is the co-primary endpoint in two Phase 3 studies (ENHANCE [ClinicalTrials.gov Identifier: NCT04313881] and VERONA [ClinicalTrials.gov Identifier: NCT04401748]); therefore, measurement of CR will form part of the primary endpoint in the proposed study (alongside measurement of AEs and DLTs). Other efficacy endpoints, including ORR (including CR, mCR,

and any HI), rate of HI, duration of progression-free survival (PFS), leukemia-free survival (LFS), undetectable disease assessed by minimal residual disease (MRD), DOR, and OS will also be evaluated to better characterize the clinical efficacy of oral decitabine/cedazuridine in combination with magrolimab.

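### This study's ORR is defined without partial response, so a PR without hematologic improvement is left out of ORR and the DOR set, and the rate is not on the ASTX727-02 definition

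*Combined protocol and SAP*

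**What the plan says.** Two places in the protocol state what ORR comprises in this study. Section 8.3.1 has "ORR (including CR, mCR, or any HI"). Section 4.2 has "Other efficacy endpoints, including ORR (including CR, mCR", and the sentence goes on to add any HI. PR is in neither list. The objectives table in Section 3.0 names the endpoint without components: "ORR, rate of HI, duration of PFS, LFS, undetectable disease assessed by MRD, DOR, and OS". Section 9.3.2 also gives none, but it restricts DOR to subjects who achieved ORR.

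Elsewhere the same abbreviation has other meanings. For ASTX727-02, the synopsis and Section 2.2 include PR: "The ORR (CR + PR + mCR + HI) was 61.7% in all treated subjects and 70.1% in subjects evaluable for response". Section 2.1 uses a narrower composite for parenteral HMAs: "overall response rate (ORR; complete response [CR] + partial response [PR]) is approximately 16" percent. For magrolimab plus azacitidine, Section 2.2 reports "The ORR was 92%, with 50% achieving a CR" and does not say what the ORR contains.

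Section 8.3.1 also says that assessment follows the IWG 2006 criteria and that response is derived by program. Table 21, which sets out those criteria, lists PR as a response and defines stable disease as falling short of PR.

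**The concern.** A programmed derivation needs an exact list of qualifying categories, and the only list given for this study leaves out a category that the protocol's own response table treats as a response. Sections 4.1 and 4.5 and Table 21 all recognise relapse after PR, so a subject could relapse from a response that never counted.

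Three things are at stake. ORR would be lower than under the four-component definition for every PR without HI. DOR would omit those same subjects. The sponsor's own monotherapy figure, the natural yardstick for a reader of the study report, would rest on a different definition.

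**Working it through.** **1. The definitions side by side**

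| Where | Applies to | CR | PR | mCR | HI |
|---|---|---|---|---|---|
| Sections 4.2, 8.3.1 | this study | yes | not listed | yes | yes |
| Synopsis, Section 2.2 | ASTX727-02, 61.7% / 70.1% | yes | yes | yes | yes |
| Section 2.1 | parenteral HMA, about 16% | yes | yes | no | no |
| Section 2.2 | magrolimab + azacitidine, 92% | not stated | not stated | not stated | not stated |

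**2. Can a PR be counted through CR or mCR?** No. In Table 21, PR requires blasts reduced by at least 50% but still above 5%. CR and mCR both require 5% or less.

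**3. Does a PR imply HI?** No. Every HI category in Table 22 requires a pretreatment cytopenia: Hgb below 11 g/dL, platelets below 100, or neutrophils below 1.0 (×10⁹/L).

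- Example A: blasts 16% to 7%, good cytogenetics, no baseline cytopenia.
  - Eligibility by Table 18: blasts above 10% score 3 and good cytogenetics score 1, with 0 for each count. IPSS-R = 3 + 1 = 4.0, which meets the 3.5 threshold.
  - PR: (16 − 7)/16 = 56%, at least 50%, and 7% is above 5%. No count was abnormal before treatment, so the count criteria add nothing, provided that the response lasts 4 weeks.
  - HI: not possible, because no pretreatment cytopenia exists.
- Example B: Hgb 10.2 to 11.3 g/dL, platelets 90 to 105, blasts 12% to 6%. Assume baseline neutrophils of at least 1.0, no peripheral blasts and no baseline transfusions.
  - IPSS-R is at least 3 + 0.5 = 3.5.
  - PR: blasts fall by 50% and remain above 5%, and both counts reach the CR level.
  - HI: the Hgb rise of 1.1 is below 1.5, and the platelet rise of 15 is below 30. The neutrophil and transfusion routes are closed by the stated assumptions.

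**4. How large could the effect be?** The only guide in the documents is ASTX727-02, where 16 subjects (12%) were not evaluable.

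- Reproducing the quoted rates: the one sample size that fits every percentage is 133 treated and 117 evaluable.
  - CR: 29/133 = 21.8%, 29/117 = 24.8%
  - mCR: 43/133 = 32.3%, 43/117 = 36.8%
  - mCR with HI: 22/133 = 16.5%, 22/117 = 18.8%
  - ORR: 82/133 = 61.7%, 82/117 = 70.1%
- The mCR-with-HI subjects cannot all be additional to CR and mCR, since 29 + 43 + 22 = 94 exceeds 82. They are read here as a subset of mCR.
- Assumption: CR, PR, mCR and HI-only are mutually exclusive best responses. Then PR + HI-only = 82 − 29 − 43 = 10 subjects, which is 10/133 = 7.5% of treated and 10/117 = 8.5% of evaluable.
- On this study's three-component definition, the reference lies between 72/133 = 54.1% (all ten are PR without HI) and 61.7% (none are). On the evaluable base it lies between 72/117 = 61.5% and 70.1%.
- If a similar share applied here, adding PR would reclassify 0 to about 8 of 100 subjects.

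**5. What does not move?** Section 9.1 sizes the trial on CR (40% against 20%), Section 9.3.2 analyses CR as primary, and the Section 9.4 futility rule counts CRs. ORR enters none of these.

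**The case against.** The best defence is that both lists are introduced by a word meaning that items are included, which need not be exhaustive. Section 8.3.1 invokes IWG 2006, where PR is a response, and Section 9.3 leaves technical detail to an SAP to be finalised before the futility analysis. No SAP text defining ORR is in the documents, so it is not established that PR will be scored as non-response. That uncertainty stands. However, two sections give the same PR-free list and none adds PR for this study, so an SAP written from them would carry the omission forward. If PR was intended, the wording still needs correcting.

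A second defence is that no ORR comparison is planned. Key secondary endpoints are not formally tested, and the ASTX727-02 figure is background from a crossover study that took in MDS/CMML or AML, whereas this trial excludes CMML. This also stands: matching the definition would remove one difference, not all of them.

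A reader might infer two stronger things that the documents do not support.

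- That every PR lasting 4 to under 8 weeks drops out, because Table 21 asks for 4 weeks and Table 22 for 8. PR duration depends on marrow blasts as well as counts, while HI depends on counts or transfusions. Counts can therefore stay improved for 8 weeks around a shorter PR. A PR that deepens to mCR or CR is counted as well.
- That all the reference rates are thrown off by the missing PR and mended by adding it. The 92% has no stated components, so a mismatch cannot be shown. The 16% is CR + PR and would still differ, because mCR and HI remain in this study's ORR.

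**Conclusion.** The point holds as a definitional defect in a secondary endpoint. Read literally, the protocol leaves a PR without HI out of ORR and out of the DOR set, and puts ORR on a different definition from the ASTX727-02 rate.

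The number of subjects affected is not in the documents and is probably small. The range of 0 to 7.5 points of all treated rests on mutually exclusive best responses in ASTX727-02. Its upper end also requires that all ten remaining responders were PRs without HI. If CR and mCR counts overlapped there, the remainder would exceed ten by the size of the overlap.

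It would go too far to call the DOR population wrong in itself. DOR follows whatever ORR definition is adopted, and the defect is the exclusion that it inherits. Nothing here touches the primary CR result, the sample size or the futility decision. It should be corrected because the correction is free and the endpoint is to be programmed.

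**What to change.** Define ORR once, as CR + PR + mCR + HI, and use that definition in Sections 3.0, 4.2, 8.3.1 and 9.3.2 and in the SAP. State in Section 9.3.2 that the DOR set is the subjects meeting that definition. Reporting the count in each component would let readers rebuild any other composite.

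If leaving out PR is deliberate, give the reason and re-score the ASTX727-02 rate on the three-component definition before setting the two side by side.

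The cost is wording only. Marrow blasts, blood counts and transfusions are already collected, and PR is already a Table 21 category. The change should be made before the SAP is finalised, which Section 9.3 places ahead of the futility analysis.

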### **8.3.2 Long-term Follow-up**

Beginning 3 months after the 30-day Safety Follow-up visit (for subjects who permanently discontinued treatment), subjects will be followed in long-term follow-up for health status information, which will be gathered every 3 months ( $\pm 2$  weeks) until death, the subject withdraws consent, the subject is lost to follow-up, or the study ends, whichever occurs first. Long-term follow-up may be accomplished through a telephone call to the subject or next of kin, contact with the local treating physician, or medical record review. If the subject did not have disease progression prior to treatment discontinuation, the absence of disease progression should be monitored according to standard practice during long-term follow-up contact. For subjects who discontinued treatment before documented disease progression and have a telephone visit, they should be asked if they have had disease progression (bone marrow blast count  $\geq 5\%$  and MDS conversion to AML) or any transfusion requirements since last contact. Follow-up contact will also permit BM biopsy reports to be obtained from subjects that discontinue treatment to receive an SCT, allowing efficacy to be followed at this stage. The investigator or designee should record the subject's survival status in the eCRF. Date of death may be collected and recorded in the EDC system from public sources in cases of subjects who withdraw consent or who are lost to follow-up. In the event of death, a death form detailing the primary cause of death must be completed for the subject.

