#### Type of Participant and Disease Characteristics

- 2) Histological confirmation of previously untreated MDS (ie, no HMA, chemotherapy, or allogenic SCT) per World Health Organization 2016 classification with  $<20\%$  BM blasts per marrow biopsy/aspirate at screening.
- 3) Projected life expectancy of at least 3 months.
- 4) Overall IPSS-R score  $\geq 3.5$  MDS (intermediate risk or higher).
- 5) Eastern Cooperative Oncology Group (ECOG) performance status (PS) of  $\leq 2$ .
- 6) Hematopoietic stem cell transplant (HSCT) eligible without any pre-arranged HSCT on Cycle 1 Day 1, or HSCT ineligible.
- 7) Hemoglobin  $\geq 9$  g/dL on the first day of drug administration, transfusions allowed.
- 8) Blood type and screen (ABO/Rh) along with extended red blood cell phenotyping or genotyping completed prior to study drug treatment.
- 9) Willing to undergo blood transfusions as per parameters of protocol and clinically necessary.
- 10) White blood cell count  $\leq 20 \times 10^3/\mu\text{L}$  prior to first dose and throughout study. Hydroxyurea can be used to achieve this goal prior to and during the first 56 days of magrolimab administration.

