**Table 21: Response Criteria in Myelodysplastic Syndromes (IWG 2006 Criteria)**

Category	Response Criteria (responses must last $\geq 4$ weeks)
CR	
 
• BM <math>\leq 5\%</math> myeloblasts with normal maturation of all cell linesa
 
• Persistent dysplasia will be noteda,b
 
• Peripheral bloodc
 
• Hgb <math>\geq 11</math> g/dL
 
• Platelets <math>\geq 100 \times 10^9/L</math>
 
• Neutrophils <math>\geq 1.0 \times 10^9/L^b</math>
 
• Blasts 0%
 

PR	All CR criteria if abnormal before treatment except: 
 
• BM blasts decreased by <math>\geq 50\%</math> over pretreatment but still <math>>5\%</math>
 
• Cellularity and morphology not relevant
 

Marrow CR	BM $\leq 5\%$ myeloblasts and decrease by $\geq 50\%$ over pretreatment b Peripheral blood: if HI responses, they will be noted in addition to marrow CR b
Stable Disease	Failure to achieve at least PR, but no evidence of progression for $>8$ weeks
Failure	Death during treatment or disease progression characterized by worsening cytopenias, increase in percentage of BM blasts, or progression to a more advanced MDS FAB subtype than pretreatment
Relapse after CR or PR	At least 1 of the following: 
 
• Return to pretreatment BM blast percentage
 
• Decrement of <math>\geq 50\%</math> from maximum remission/response levels in granulocytes or platelets
 
• Reduction in Hgb concentration by <math>\geq 1.5</math> g/dL or transfusion dependenced
 

Cytogenetic Response	Complete: Disappearance of chromosomal abnormality without appearance of new ones Partial: At least 50% reduction of the chromosomal abnormality

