Disease Progression	For patients with: 
 
• Less than 5% blasts: <math>\geq 50</math> increase in blasts to <math>>5\%</math> blasts
 
• 5%-10% blasts: <math>\geq 50\%</math> increase in blasts to <math>>10\%</math> blasts
 
• 10%-20% blasts: <math>\geq 50\%</math> increase in blasts to <math>>20\%</math> blasts
 
• 20%-30% blasts: <math>\geq 50\%</math> increase in blasts to <math>>30\%</math> blasts
 
 Any of the following: 
 
• At least 50% decrement from maximum remission/response in granulocytes or platelets
 
• Reduction in Hgb by <math>\geq 2</math> g/dLd
 
• Transfusion dependenced
 

BM=bone marrow; CR=complete response; FAB=French-American-British classification; Hgb=hemoglobin; HI=hematologic improvement; IWG=International Working Group; MDS=myelodysplastic syndromes; PR=partial remission.

a Dysplastic changes should consider the normal range of dysplastic changes.

b Modification to IWG response criteria

c In some circumstances, protocol therapy may require the initiation of further treatment (eg, consolidation, maintenance) before the 4-week period. Such patients can be included in the response category into which they fit at the time the therapy is started. Transient cytopenias during repeated chemotherapy courses should not be considered as interrupting durability of response, as long as they recover to the improved counts of the previous course.

d Impact of anemia must be deemed disease-related and not due to study treatment.

Source: [Cheson et al 2006](#)

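### The long-term follow-up telephone question in Section 8.3.2 defines progression differently from Table 21 and leaves out relapse, so PFS or DOR events could be missed, falsely recorded or misdated if its answers are used

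*Combined protocol and SAP*

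**What the plan says.** Section 8.3.2 covers subjects who have permanently stopped treatment. Where they had not progressed, "the absence of disease progression should be monitored according to standard practice during long-term follow-up contact". A more specific instruction is then given for one group, introduced by the words "For subjects who discontinued treatment before documented disease progression and have a telephone visit". Of this group the section requires that "they should be asked if they have had disease progression (bone marrow blast count" is 5% or more; after that threshold the wording is "and MDS conversion to AML) or any transfusion requirements since last contact". The same section allows the contact to be with the subject, next of kin or the local physician, or to be a record review.

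Table 21 (Section 10.6) sets out the response criteria. Its Disease Progression row requires a rise in blasts of at least 50% that also passes 5%, 10%, 20% or 30%, depending on the blast band. Alternatively it accepts any of these: "At least 50% decrement from maximum remission/response in granulocytes or platelets", a hemoglobin fall of at least 2 g/dL, or transfusion dependence. Footnote d requires that anemia be disease-related. A separate row gives relapse after CR or PR, whose first criterion is "Return to pretreatment BM blast percentage".

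Section 8.3.1 says that disease assessment follows the IWG 2006 criteria and adds: "Response will be assessed by the investigator and derived programmatically based on the 2006 IWG criteria". Section 4.1 counts treatment failure and relapse after PR or CR as progression when it says how long treatment may continue. Section 9.3.2 plans Kaplan-Meier analyses that include PFS and DOR, but the documents define neither the events nor the censoring.

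**The concern.** PFS and DOR need one event definition on and off treatment. The telephone question gives sites a different one for subjects who come off treatment without progression, including those who go to transplant. It uses a fixed 5% blast level, joins it to AML conversion, does not ask about neutrophils, platelets or hemoglobin, and does not mention relapse, which is the event that ends a response.

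A wrong call could also stop data collection. Under Table 1, footnote e, disease assessments in long-term follow-up end once blood or marrow shows progression or relapse; under footnote r, transfusion recording ends once progression is documented. If a site takes a marrow report of 5% or more as progression because of the bracket, later data may not be collected, and no analysis rule could recover them.

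**Working it through.** The plan gives no figure to reproduce. The check compares the bracket in Section 8.3.2 with the blast part of Table 21's Disease Progression row.

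**Inputs and assumptions.** Entry requires under 20% "BM blasts per marrow biopsy/aspirate at screening" (Section 5.1), so a subject may start anywhere below that. Assumptions of mine: AML conversion means marrow blasts of at least 20%; the rise is measured from the pretreatment value; exactly 10% belongs to the 5%-10% band; and the rise in the lowest band, printed without a unit, is 50 percent.

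**Rules.** With pretreatment blasts *b* and current blasts *f*:
- Table 21: *f* ≥ 1.5*b*, and *f* > 5% if *b* < 5%, *f* > 10% if *b* is 5% to 10%, *f* > 20% if *b* is above 10%.
- Bracket read as *and*: *f* ≥ 5% and *f* ≥ 20%, which reduces to *f* ≥ 20%. The 5% level does no work.
- Bracket read as *or*: *f* ≥ 5% or *f* ≥ 20%, which reduces to *f* ≥ 5%. The AML part does no work.

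| Blasts, pretreatment to now | Table 21 blast criterion | *and* | *or* |
|---|---|---|---|
| 2% to 8% | met (+300%, above 5%) | no | yes |
| 6% to 12% | met (+100%, above 10%) | no | yes |
| 8% to 14% | met (+75%, above 10%) | no | yes |
| 8% to 8% | not met (no rise) | no | yes |
| 12% to 6% | not met (50% fall) | no | yes |
| 15% to 21% | not met (+40%) | yes | yes |
| 18% to 22% | not met (+22%) | yes | yes |

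The 12% to 6% case meets the blast part of Table 21's PR row: a fall of at least half, still above 5%. Every PR has blasts above 5% by definition, so the *or* reading would label any partial responder as progressed.

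**All integer combinations.** For *b* from 0% to 19% and *f* from 0% to 40% there are 20 × 41 = 820 combinations, of which 503 meet the Table 21 blast criterion.
- *and*: 387 agree as progression, 116 are missed, 33 are extra, 284 agree as no progression (387 + 116 + 33 + 284 = 820).
- *or*: 503 agree as progression, 0 are missed, 217 are extra, 100 agree as no progression (503 + 217 + 100 = 820).

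The combinations are not weighted by how likely they are, so these counts are not error rates. They show only that neither reading reproduces Table 21.

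**Relapse.** Take a subject with 12% blasts at entry, a CR at 3%, and 12% again in follow-up. That meets Table 21's relapse row. It does not meet the progression row's blast criterion measured from pretreatment (12% against 12%, no rise), and the *and* reading also gives no. A fix that named only the progression row could therefore still miss this event.

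**Other criteria.** A halving of granulocytes or platelets, or a hemoglobin fall, appears nowhere in the question. Transfusion is asked about, but any transfusion requirement is broader than transfusion dependence, and the question does not separate disease-related anemia as footnote d does.

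**The case against.** The strongest reply is that the telephone question is one prompt among several safeguards.

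- The question goes on to ask about transfusions, and footnote r of Table 1 has transfusions recorded in long-term follow-up until progression. Part of Table 21's non-blast criteria is therefore captured.
- Footnote e provides transfusion, hematology and/or marrow assessments for these same subjects until blood or marrow shows progression or relapse. Section 4.1 also continues response assessment after treatment stops.
- Section 8.3.1 ties response to programmed IWG 2006 criteria, under which a fall from 12% to 6% could not come out as progression.
- The *or* reading is not what the text says.
- PFS and DOR are secondary, with no formal test.

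Most of this stands, and it limits the consequence. A reader might infer that every post-treatment progression short of AML goes unrecorded, or that the later part of the PFS and DOR curves will be wrong. The documents do not support either: other assessments are planned, and nothing makes the telephone answer the event or its date.

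The conflict remains, however. Footnote e says and/or, allows visits by telephone, and fixes no marrow or CBC schedule, while Section 8.3.2 leaves monitoring to standard practice. At a given contact the telephone answer may be the only information on progression, and a yes or no gives the program no blast percentage or counts to work from. The *or* reading is an inference, but a site could reach it because the literal *and* leaves the 5% level with no function.

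**Conclusion.** The bracket in Section 8.3.2 contradicts Table 21 on either reading, does not ask about neutrophils, platelets or hemoglobin, and omits relapse after CR or PR. PFS and DOR events could be missed, falsely recorded or misdated, but only if telephone answers feed those endpoints or are used to end disease assessment. The documents neither say so nor rule it out.

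Those exposed are subjects who stop treatment before documented progression and are contacted by telephone. The documents give no number for this group, so no error rate can be stated. The direction of any error depends on the reading: the literal one mainly misses blast progression, the looser one adds false events. The blast examples rest on the assumptions listed with the check; the missing count and relapse criteria do not depend on them. The CR rate, the sample size of about 100 and the futility rule at about 40 subjects are unaffected. This is worth correcting before follow-up data accrue, but it does not threaten the primary analysis.

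**What to change.** Reconcile the two places:

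1. In Section 8.3.2, replace the bracketed definition with a reference to disease progression, or relapse after CR or PR, per Table 21.
2. Record AML conversion as its own dated item, which also serves leukemia-free survival.
3. At each contact, obtain whatever dated marrow, CBC and transfusion records exist, through the physician contact or record review that the section already allows, and derive events with the same IWG 2006 program.
4. State in the SAP that a telephone-only report without source data does not by itself set a PFS or DOR event, and how such subjects are handled.

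This needs changes to protocol, eCRF and SAP wording and adds no study visit or procedure. It is not entirely free: sites will have to retrieve records for some subjects, since a call to the subject or next of kin will rarely yield blast percentages or counts.
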